Selinexor-induced anemia may contribute to dizziness, confusion, syncope and/or fatigue, particularly in elderly patients and patients who are at greater risk of cognitive sequelae. Per NCCN Guidelines, treatment with RBC transfusions and/or growth factors, per institutional guidelines, should be considered for patients with symptomatic anemia.

Other Adverse Events Observed during Studies

Vision Blurred and Cataracts

Patients reporting blurry vision or other visual changes should be evaluated by an ophthalmologist. Nearly all cases of treatment emergent visual changes have not been associated with objective findings. Changes in lens prescriptions and/or wetting drops may improve vision. Blurred vision associated with selinexor use is typically self-limited, and dosing can usually be maintained at the same level and frequency.

Patients who are at risk of cataract formation, or have cataracts present at baseline, should be monitored for changes in lens opacity. If changes in lens opacity are observed, the patient should be evaluated by an ophthalmologist. In selinexor clinical studies, several patients have undergone cataract surgery with minimal to no interruption of selinexor dosing and without complications.

Hyponatremia

Investigators should rule out the possibility of pseudo-hyponatremia due to elevated glucose (or monoclonal protein) levels. Abnormal serum sodium levels should be corrected. Adequate fluid and caloric intake, including electrolyte-rich beverages instead of plain water, has led to reversal of hyponatremia. Diuretic use should be addressed and possibly stopped, and salt supplements should be considered. If hyponatremia persists, cardiac, hepatic, adrenal, renal and thyroid disorders, along with the Syndrome of Inappropriate Antidiuretic Hormone Secretion (SIADH), and Fanconi syndrome should be ruled out.

Infection

Appropriate broad-spectrum intravenous antibiotics and antifungal agents should be started immediately in patients who develop fever or other signs of systemic infection. Selinexor should be suspended in any patient with Grade 4 infection or sepsis (even in the absence of documented infection) until the patient's clinical condition is stabilized. Selinexor can then be re-started at the same dose once the patient's clinical status has stabilized, even in the setting of continued intravenous antibacterial or other anti-microbial

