agents (see section 6.1.3). Selinexor is not known to have any drug interactions with standard antimicrobials.

Dose Reduction Guidelines

Dose reductions and/or schedule modifications are allowed in order to optimize the antitumor activity and tolerability of selinexor. For some AEs, dose interruption and/or reduction is recommended. See **table 2** for pre-specified dose modifications for AEs related to study treatment and see **table 3** for dose reduction and interruption recommendations. Please note, however, that investigators should refer to specific dose reduction and interruption guidance within each protocol for the most up-to-date recommendations for each study.

While drug-related major organ toxicities are not prominent, there are a number of constitutional side effects (and thrombocytopenia) that can limit dosing with selinexor. Therefore, patients should also be treated with supportive care to reduce toxicities. In addition, it should be noted that the constitutional side effects often attenuate over the first 4 to 6 weeks of dosing. Finally, some patients with rapid tumor responses experience significant fatigue, nausea, malaise and/or asthenia after 1 or more doses of selinexor. This effect has not been associated with typical markers of tumor lysis syndrome, but if suspected, assessment of tumor response is strongly recommended in order to better inform treatment recommendations.

The CTCAE v 4.03 is used for grading the severity of AEs; the therapy modifications described in Table 3 below are applied according to this severity grading. Toxicity will be documented as described in Section 7. If more than 1 type of toxicity occurs concurrently, the most severe grade will determine the modification.

Each dose modification or treatment delay, as well as the reason, must be documented.

Tumour lysis syndrome

As of 31 March 2019, selinexor treatment-emergent TLS has been reported in a total of 8 patients including 6 SAEs. Four were from selinexor CSTs, 2 from IST, and 2 from EAP.

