6.2.2 Dose Adjustment Guidelines for Selinexor Related Toxicities

All selinexor related non-hematological toxicities except those mentioned in the table below should be handled as follows:

Interrupt selinexor dosing in case of grade ≥ 3 non-hematological toxicity and resume dosing when resolved to grade 1 or less. Reduce selinexor dose by one dose level.

Table 3. Suggested Supportive Care and Dose Adjustment Guidelines for AEs Related to Selinexor (according to IB v 9)

Adverse Event	Occurrence	Action
Hematologic Adverse Events		
Thrombocytopenia		
Platelet count $25 \times 10^9/L$ to $<75 \times 10^9/L$	Any	
 Reduce selinexor by 1 dose level (see Table 2) Consider additional supportive care and discuss with Sponsor-Investigator
Platelet count $25 \times 10^9/L$ to $<75 \times 10^9/L$ with concurrent bleeding	Any	
 Interrupt selinexor Restart selinexor at 1 dose level lower after bleeding has resolved (see Table 2) Consider additional supportive care and discuss with Sponsor-Investigator
Platelet count $<25 \times 10^9/L$	Any	
 Interrupt selinexor Monitor until platelet count returns to at least $50 \times 10^9/L$ Restart selinexor at 1 dose level lower (see Table 2) Consider additional supportive care and discuss with Sponsor-Investigator
Neutropenia		

ANC 0.5 to $1.0 \times 10^9/L$ without fever	Any	
 Initiate growth factor support
ANC $<0.5 \times 10^9/L$ OR febrile neutropenia	Any	
 Interrupt selinexor Monitor until ANC returns to $\geq 1.0 \times 10^9/L$ Restart selinexor at 1 dose level lower (see Table 2) Initiate growth factor support
Anemia		
Hb $<8.0 \text{ g/dL}$	Any	
 Administer blood transfusions and/or other treatments per clinical guidelines

Adverse Event	Occurrence	Action
Life-threatening consequences (urgent intervention indicated)	Any	
 Interrupt selinexor Monitor until Hb returns to $\geq 8.0 \text{ g/dL}$ Restart selinexor at 1 dose level lower (see Table 2) Administer blood transfusions and/or other treatments per clinical guidelines
Nonhematologic Adverse Events		
Hyponatremia		

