Sodium $\leq 130 \text{ mmol/L}$	First	
 Interrupt selinexor and provide appropriate supportive care Monitor until sodium returns to $>130 \text{ mmol/L}$ Restart selinexor at same dose
	Second	
 Interrupt selinexor and provide appropriate supportive care Monitor until sodium returns to $>130 \text{ mmol/L}$ Restart selinexor at 1 dose lower (see Table 2)
Fatigue		
Grade 2 lasting >7 days OR Grade 3	Any	
 Interrupt selinexor and provide appropriate supportive care Add methylphenidate Monitor until fatigue resolves to Grade 1 or baseline Restart selinexor at 1 dose level lower (see Table 2)
Nausea and Vomiting		

Grade 1 or 2 nausea OR Grade 1 or 2 vomiting	Any	
 Maintain selinexor and initiate additional anti-nausea medications
Grade 3 nausea OR Grade ≥ 3 vomiting	Any	
 Interrupt selinexor Monitor until nausea or vomiting has resolved to \leqGrade 2 or baseline. Initiate additional anti-nausea medications Restart selinexor at 1 dose level lower (see Table 2)
Adverse Event	Occurrence	Action
Diarrhea		
Grade 2	First	
 Maintain selinexor and institute supportive care
	Second and subsequent	
 Reduce selinexor by 1 dose level (see Table 2) Institute supportive care
Grade ≥ 3	Any	
 Interrupt selinexor and institute supportive care Monitor until diarrhea resolves to Grade ≤ 2 Restart selinexor at 1 dose level lower (see Table 2)
Weight Loss and Anorexia		
Weight loss of 10% to $<20\%$ OR anorexia associated with significant weight loss or malnutrition	Any	
 Interrupt selinexor and institute supportive care Monitor until weight returns to $>90\%$ of baseline weight Restart selinexor at 1 dose level lower (see Table 2)
Other Nonhematologic Adverse Events		
Grade 3 or 4	Any	
 Interrupt selinexor and institute supportive care Monitor until resolved to \leqGrade 2 Restart selinexor at 1 dose level lower (see Table 2)

Conditions Not Requiring Selinexor Dose Reduction

The following conditions are exceptions to the dose-modification guidelines. Selinexor does not need to be held for alopecia of any grade, or forelectrolyte or serum analyte (e.g., urate) abnormalities that are reversible with standard interventions

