Selinexor Dose Adjustment in the Setting of Infection

In patients who develop fever or other signs of systemic infection, appropriate antimicrobial should be initiated immediately. Selinexor should be withheld in any patient with active uncontrolled infection, any Grade 4 infection or sepsis (even in the absence of documented infection) until the patient is clinically stable. After the infection has stabilized clinically or resolved, Selinexor treatment may continue at the original dose. Missed doses will not be replaced. Patients may continue on antibiotics for prolonged periods while re-initiating their Selinexor regimen at the discretion of the investigator. Selinexor is not known to have any drug interactions with standard antimicrobials.

Prophylactic antibiotics are permitted concurrently with Selinexor treatment, but are not recommended for most patients. Patients with a history of recurrent infections or those at high risk for specific infections may continue their prophylactic antimicrobial regimens without modification when initiating selinexor therapy. In a randomised study in old patients with acute myeloid leukemia (AML), sepsis occurred more frequently in patients receiving Selinexor compared with patients receiving physician's choice of therapy.

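### When toxicities coincide, the highest grade rather than the strictest action decides, so a recommended dose reduction can drop out

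*Combined protocol and SAP*

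**What the plan says.** Section 6.2.1, under Dose Reduction Guidelines, explains that toxicity is graded by CTCAE v 4.03 and that the modifications in Table 3 follow that grading. It then adds: "If more than 1 type of toxicity occurs concurrently, the most severe grade will determine the modification". No clause in 6.2.1 or 6.2.2 says that the stricter of two actions prevails.

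The actions that can meet under this sentence are:

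- **Infection, 6.2.1.** Dosing is suspended for Grade 4 infection or sepsis until the patient is stable. Then: "Selinexor can then be re-started at the same dose".
- **Infection, 6.2.2.** "Selinexor should be withheld in any patient with active uncontrolled infection, any Grade 4 infection or sepsis". Afterwards: "After the infection has stabilized clinically or resolved, Selinexor treatment may continue at the original dose".
- **Diarrhea of Grade 3 or higher, Table 3, any occurrence.** Hold, wait for Grade 2 or lower, then "Restart selinexor at 1 dose level lower (see Table 2". Grade 3 fatigue, Grade 3 nausea and vomiting of Grade 3 or higher also restart one level lower.
- **Sodium at or below 130 mmol/L, first occurrence, Table 3.** Hold, correct, then "Restart selinexor at same dose".
- **Grade 2 diarrhea, second and later occurrences, Table 3.** "Reduce selinexor by 1 dose level (see Table 2", with no hold.

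Two general provisions also bear on sepsis. The lead-in to 6.2.2 reduces by one level after any selinexor-related non-hematological toxicity of Grade 3 or higher that Table 3 does not name. The last row of Table 3 does the same for other nonhematologic events of Grade 3 or 4.

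**The concern.** Ranking coinciding toxicities by grade is a sound shortcut only when the action never becomes milder as the grade rises. Across different toxicities in this protocol it can. Grade 4 infection or sepsis has a hold without a required reduction, while several Grade 3 events have a hold with a reduction. If the Grade 4 event decides, the reduction attached to the Grade 3 event is no longer called for. The sicker patient may then resume at a higher dose than a patient with the Grade 3 event alone.

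What is at stake is patient safety and uniform dosing across the US and EU sites whose data are pooled. Section 1.1.5 shows that dose modification matters in this study: 10 of the first 16 patients needed a dose reduction or discontinuation for toxicity.

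**Working it through.** **Step 1. Reproduce the plan's own figure.** The treatment schema in the synopsis gives 6 doses per cycle. Two doses per week × 3 dosing weeks = 6, which agrees. The protocol states no totals in mg per cycle, so they are derived next.

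**Step 2. Dose per 28-day cycle.** Formula: mg per dosing week × 3 weeks, with the levels of Table 2.

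| Level now | mg per cycle | One level lower | Difference |
|---|---|---|---|
| 0 | (40 + 40) × 3 = 240 | 180 | 60 (60/180 = 33%) |
| -1 | (20 + 40) × 3 = 180 | 120 | 60 (60/120 = 50%) |
| -2 | 40 × 3 = 120 | 60 | 60 (60/60 = 100%) |
| -3 | 20 × 3 = 60 | 0 (discontinue) | 60 mg versus no treatment |

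**Step 3. Grade 3 diarrhea alone, from level 0.** The diarrhea row applies: hold, then restart at level -1, which is 180 mg per cycle.

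**Step 4. Grade 3 diarrhea with Grade 4 sepsis, from level 0, both settling during the hold.** The result depends on which text is taken to govern. I take the original dose in 6.2.2 to mean the dose before the hold, in line with 6.2.1.

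| Reading | Restart, mg per cycle |
|---|---|
| The sentence reaches the infection text, and that text governs a selinexor-related sepsis | 240 permitted |
| The 6.2.2 lead-in governs the sepsis | 180 |
| The Table 3 row for other nonhematologic events governs the sepsis | 180 |
| The sentence ranks Table 3 rows only, and infection has no row of its own | 180 |
| The sepsis is judged unrelated to selinexor, so it is not a competing toxicity | 180 |

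If the diarrhea outlasts the hold for infection, its own row still applies and the restart is again 180 mg.

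**Step 5. A possible second case inside Table 3: first sodium at or below 130 mmol/L with a second Grade 2 diarrhea.** Table 3 prints no grade for sodium, so the grade is an assumption and all values are shown.

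- Sodium at Grade 3 or 4: the sodium row decides, and the diarrhea reduction drops out (240 instead of 180 mg from level 0).
- Sodium at Grade 2: the grades tie, and the sentence does not decide.
- Sodium at Grade 1: the diarrhea row decides, and the hold for sodium drops out.

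This case also depends on the list of conditions that need no dose reduction, after Table 3. It exempts electrolyte abnormalities that standard measures can reverse. If that exemption covers the sodium value, sodium does not compete with the diarrhea row and no conflict arises.

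**The case against.** The strongest reply is that the 240 mg result needs three contestable steps.

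- **Scope.** The sentence closes a paragraph about Table 3, and infection is not in that table. Letting free text elsewhere displace a Table 3 row goes beyond the plainest reading.
- **Competing rules.** The 6.2.2 lead-in and the last row of Table 3 are worded broadly enough to reach a related Grade 4 sepsis, and both reduce.
- **Relatedness.** The infection text covers any patient, whereas Tables 2 and 3 concern events related to study drug.

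All three stand as limits. They do not remove the point. The infection text names Grade 4 infection and sepsis, appears twice, and sits partly in a section headed "Dose Adjustment Guidelines for Selinexor Related Toxicities". It is therefore a reasonable candidate for the governing rule, and nothing tells a site which reading to use.

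The wording is also soft: the infection restart is permissive, and Table 3 is titled as suggested guidance. That stands too. A reader might infer that adding sepsis forces the dose up to 240 mg, or that an investigator who reduces would breach the protocol. The documents support neither. The patient would only resume the previous dose, and a reduction stays open to the investigator.

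A reader might also take the 10 of 16 in section 1.1.5 as a sign that the combination is common. It is not evidence of that. It covers all toxicity-driven reductions and discontinuations under the initial 60 mg design. The same section lists severe pneumonia among the toxicities that led to dose reduction, so doses were being lowered in the setting of severe infection. Section 6.2.1 describes selinexor diarrhea as typically low grade, so the combination may well be rare.

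**Conclusion.** The point holds as a minor weakness in a safety rule. Grade and strictness of action do not line up in this protocol, and the sentence in 6.2.1 follows grade. Read literally, it can remove a recommended one-level reduction when a more severe toxicity is added. The size is one dose level, 60 mg per cycle: 240 mg permitted against 180 mg from level 0, and a larger relative gap from lower levels.

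The diarrhea and sepsis case rests on four assumptions: the sentence reaches beyond Table 3; the infection text governs; the sepsis counts as selinexor-related; and the diarrhea settles during the hold. If any one fails, the restart is 180 mg. The sodium case is weaker, because it turns on an unprinted grade and on how the electrolyte exemption is read.

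The documents give no frequency for either combination, and none is claimed. The primary endpoint, error rates and analysis are unaffected.

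**What to change.** Replace the sentence in 6.2.1 with one to this effect:

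*When two or more toxicities coincide, apply the strictest action called for by any applicable row of Table 3, the 6.2.2 lead-in or the infection guidance. Hold dosing if any of them calls for a hold; restart only when every toxicity that requires a hold has met its own restart condition; and reduce by one dose level in total if any of them calls for a reduction.*

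This gives 180 mg per cycle in the diarrhea and sepsis case from level 0 under every reading set out above. In the sodium case it keeps the diarrhea reduction whatever the sodium grade. Limiting the reduction to one level in total prevents coinciding events from stacking reductions.

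The cost is one sentence in the next amendment. Affected patients would restart one level lower, which is 60 mg less per cycle (or discontinuation from level -3), and some holds would last longer because every restart condition must be met.

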6.2.2 Dose Adjustment Guidelines for Selinexor Related Toxicities

All selinexor related non-hematological toxicities except those mentioned in the table below should be handled as follows:

Interrupt selinexor dosing in case of grade ≥ 3 non-hematological toxicity and resume dosing when resolved to grade 1 or less. Reduce selinexor dose by one dose level.

Table 3. Suggested Supportive Care and Dose Adjustment Guidelines for AEs Related to Selinexor (according to IB v 9)

Adverse Event	Occurrence	Action
Hematologic Adverse Events		
Thrombocytopenia		
Platelet count $25 \times 10^9/L$ to $<75 \times 10^9/L$	Any	
 Reduce selinexor by 1 dose level (see Table 2) Consider additional supportive care and discuss with Sponsor-Investigator
Platelet count $25 \times 10^9/L$ to $<75 \times 10^9/L$ with concurrent bleeding	Any	
 Interrupt selinexor Restart selinexor at 1 dose level lower after bleeding has resolved (see Table 2) Consider additional supportive care and discuss with Sponsor-Investigator
Platelet count $<25 \times 10^9/L$	Any	
 Interrupt selinexor Monitor until platelet count returns to at least $50 \times 10^9/L$ Restart selinexor at 1 dose level lower (see Table 2) Consider additional supportive care and discuss with Sponsor-Investigator
Neutropenia		

ANC 0.5 to $1.0 \times 10^9/L$ without fever	Any	
 Initiate growth factor support
ANC $<0.5 \times 10^9/L$ OR febrile neutropenia	Any	
 Interrupt selinexor Monitor until ANC returns to $\geq 1.0 \times 10^9/L$ Restart selinexor at 1 dose level lower (see Table 2) Initiate growth factor support
Anemia		
Hb $<8.0 \text{ g/dL}$	Any	
 Administer blood transfusions and/or other treatments per clinical guidelines

Adverse Event	Occurrence	Action
Life-threatening consequences (urgent intervention indicated)	Any	
 Interrupt selinexor Monitor until Hb returns to $\geq 8.0 \text{ g/dL}$ Restart selinexor at 1 dose level lower (see Table 2) Administer blood transfusions and/or other treatments per clinical guidelines
Nonhematologic Adverse Events		
Hyponatremia		
Sodium $\leq 130 \text{ mmol/L}$	First	
 Interrupt selinexor and provide appropriate supportive care Monitor until sodium returns to $>130 \text{ mmol/L}$ Restart selinexor at same dose
	Second	
 Interrupt selinexor and provide appropriate supportive care Monitor until sodium returns to $>130 \text{ mmol/L}$ Restart selinexor at 1 dose lower (see Table 2)
Fatigue		
Grade 2 lasting >7 days OR Grade 3	Any	
 Interrupt selinexor and provide appropriate supportive care Add methylphenidate Monitor until fatigue resolves to Grade 1 or baseline Restart selinexor at 1 dose level lower (see Table 2)
Nausea and Vomiting		

Grade 1 or 2 nausea OR Grade 1 or 2 vomiting	Any	
 Maintain selinexor and initiate additional anti-nausea medications
Grade 3 nausea OR Grade ≥ 3 vomiting	Any	
 Interrupt selinexor Monitor until nausea or vomiting has resolved to \leqGrade 2 or baseline. Initiate additional anti-nausea medications Restart selinexor at 1 dose level lower (see Table 2)
Adverse Event	Occurrence	Action
Diarrhea		
Grade 2	First	
 Maintain selinexor and institute supportive care
	Second and subsequent	
 Reduce selinexor by 1 dose level (see Table 2) Institute supportive care
Grade ≥ 3	Any	
 Interrupt selinexor and institute supportive care Monitor until diarrhea resolves to Grade ≤ 2 Restart selinexor at 1 dose level lower (see Table 2)
Weight Loss and Anorexia		
Weight loss of 10% to $<20\%$ OR anorexia associated with significant weight loss or malnutrition	Any	
 Interrupt selinexor and institute supportive care Monitor until weight returns to $>90\%$ of baseline weight Restart selinexor at 1 dose level lower (see Table 2)
Other Nonhematologic Adverse Events		
Grade 3 or 4	Any	
 Interrupt selinexor and institute supportive care Monitor until resolved to \leqGrade 2 Restart selinexor at 1 dose level lower (see Table 2)

Conditions Not Requiring Selinexor Dose Reduction

The following conditions are exceptions to the dose-modification guidelines. Selinexor does not need to be held for alopecia of any grade, or forelectrolyte or serum analyte (e.g., urate) abnormalities that are reversible with standard interventions

Selinexor Dose Adjustment in the Setting of Infection

In patients who develop fever or other signs of systemic infection, appropriate antimicrobial should be initiated immediately. Selinexor should be withheld in any patient with active uncontrolled infection, any Grade 4 infection or sepsis (even in the absence of documented infection) until the patient is clinically stable. After the infection has stabilized clinically or resolved, Selinexor treatment may continue at the original dose. Missed doses will not be replaced. Patients may continue on antibiotics for prolonged periods while re-initiating their Selinexor regimen at the discretion of the investigator. Selinexor is not known to have any drug interactions with standard antimicrobials.

Prophylactic antibiotics are permitted concurrently with Selinexor treatment, but are not recommended for most patients. Patients with a history of recurrent infections or those at high risk for specific infections may continue their prophylactic antimicrobial regimens without modification when initiating selinexor therapy. In a randomised study in old patients with acute myeloid leukemia (AML), sepsis occurred more frequently in patients receiving Selinexor compared with patients receiving physician's choice of therapy.

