Dose level -1	20 mg day 1 plus 40 mg day 2, 3 weeks on/1 week off
Dose level -2	40 mg once weekly, 3 weeks on/1 week off
Dose level -3	20 mg once weekly, 3 weeks on/1 week off
Dose level -4	Discontinue Dosing

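### Section 6.2.2 sets two different recovery grades for restarting selinexor after a related grade 3 or 4 non-hematological toxicity with no named row in Table 3, and does not say which governs

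*Combined protocol and SAP*

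**What the plan says.** Section 6.2.2 holds two instructions for the same kind of event.

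- **Running text.** It opens with its scope: "All selinexor related non-hematological toxicities except those mentioned in the table below should be handled as follows". The rule is then "Interrupt selinexor dosing in case of grade ≥ 3 non-hematological toxicity and resume dosing when resolved to grade 1 or less", followed by a reduction of one dose level.
- **Table 3, last row.** The row is titled "Other Nonhematologic Adverse Events" and applies to grade 3 or 4, at any occurrence. Dosing is interrupted with supportive care. The recovery instruction begins "Monitor until resolved to" and sets the limit at grade 2 or lower. Selinexor then restarts one dose level lower.

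The non-hematologic categories with rows of their own are hyponatremia, fatigue, nausea and vomiting, diarrhea, and weight loss with anorexia.

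The dose levels are in Table 2 (Section 6.2.1). From the starting dose, one level down is "20 mg day 1 plus 40 mg day 2, 3 weeks on/1 week off". From level -3, the next step is to stop dosing.

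**The concern.** An investigator whose patient has a related grade 3 or 4 toxicity without a named row finds two recovery thresholds in one section. Two sites could each follow the protocol and re-expose similar patients at different stages of recovery.

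Cerebellar toxicity shows why this matters. Section 7.3 lists acute cerebellar syndrome as an adverse event of special interest and sets a reporting rule for grade 3 or higher. It has no named row in Table 3, and no dosing guidance appears elsewhere.

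There is also a compliance problem. Section 9.7 requires significant deviations to be recorded and reported. A restart at grade 2 is compliant under the table row and a deviation under the text. The discontinuation provisions in Sections 3.1.2 and 5.4 let the investigator stop treatment, but they set no threshold for resuming it.

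**Working it through.** No formula applies. The check sets the two rules side by side and looks for anything that ranks them.

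**Step 1: compare the rules.**

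| Element | Section 6.2.2 text | Table 3 catch-all row |
|---|---|---|
| Trigger | grade 3 or higher | grade 3 or 4 |
| First action | interrupt | interrupt |
| Recovery needed to restart | grade 1 or lower | grade 2 or lower |
| Dose on restart | one level lower | one level lower |

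Only the recovery grade differs in practice. The triggers differ in wording, but grade 5 means a fatal event (Section 7.4), so no restart question arises above grade 4.

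**Step 2: find where they diverge.**

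| Current grade | Text | Table | Same? |
|---|---|---|---|
| 3 or more | hold | hold | yes |
| 2 | hold | restart one level lower | no |
| 1 or less | restart one level lower | restart one level lower | yes |

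They diverge in one of the three states. The divergence exists for events at dose levels 0, -1 and -2. At level -3 both rules lead to level -4, where dosing stops, so there is none.

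**Step 3: test the exception clause.** The text rule leaves out toxicities mentioned in the table. There are two readings.

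- If the catch-all row is a mention, every otherwise unnamed grade 3 or 4 toxicity goes to the table. The text rule, which starts at grade 3, then has nothing left to govern.
- If only individually named toxicities are mentioned, the text and the catch-all row cover the same events and conflict directly.

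**Step 4: look for precedence elsewhere.**

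- The dose reduction guidance in Section 6.2.1 says the Table 3 modifications are applied by severity grade. It also calls the table's content recommendations and sends investigators to the guidance in each protocol. Both rules are in this protocol.
- Table 3's heading describes its content as suggested and taken from version 9 of the Investigator's Brochure, while the text says what should be done. The wording therefore pulls both ways.
- The named rows show no common threshold to infer from: fatigue must return to grade 1 or baseline, nausea and vomiting to grade 2 or baseline, and diarrhea to grade 2.

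None of this ranks the two rules.

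**Step 5: bound the scope.** Some events are at least partly handled elsewhere: infection (Sections 6.2.1 and 6.2.2), blurred vision (6.2.1), renal effects (6.2.1 and 6.2.3), and alopecia and reversible electrolyte or analyte abnormalities (the exceptions after Table 3). That guidance does not plainly cover every grade 3 or 4 case, so these events are not wholly outside the problem.

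**The case against.** The strongest reply is that the exception clause works as written. Table 3 does mention other non-hematologic events, Section 6.2.1 directs the reader to Table 3 and says it is applied, and that section never cites the text rule. On this view the table governs and the text sentence is merely surplus. The reading is workable. It is not stated anywhere, however, and it leaves a directive sentence with no grade 3 or 4 toxicity to direct. An investigator has no reason to assume that was intended.

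The second reply concerns reach, and it largely stands. Section 1.1.5 reports that ten of the first 16 patients needed a dose reduction or stopped for toxicity, so a reader might infer that the conflict touches most dose modifications. The documents do not support that. The typical causes listed there are nausea, vomiting, loss of appetite, fatigue, thrombocytopenia and pneumonia, all with a Table 3 category or infection guidance. The most common events in Section 1.1.4.2 also have rows. No documented event in this trial is shown to fall in the disputed class.

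A reader might also extend the point to the severity ranges of two named rows. The fatigue row covers "Grade 2 lasting >7 days OR Grade 3"; a gap would need a fatigue grade above 3, which the documents do not show. The other row starts at "Weight loss of 10% to" and stops below 20%. A larger loss is a separate small omission: weight loss is named in the table, so it is neither left to the text rule nor an unnamed event.

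**Conclusion.** The point holds as an internal inconsistency. Section 6.2.2 gives two recovery thresholds for related grade 3 or 4 non-hematological toxicities without a named row, and no section says which prevails. Confidence that the thresholds differ is high.

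The size is modest: one recovery state, at three of the four active dose levels, in a group of events whose frequency the documents do not give. The cerebellar example assumes a related event that improves to grade 2; no incidence is stated.

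Two stronger inferences are not supported. A reader might turn the divergence into a cumulative dose difference, but that needs the time spent at grade 2, which the documents do not give. A reader might also infer an effect on the response rate, the sample size or the error rates; nothing in the documents shows one. The consequence is for consistent safety management.

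**What to change.** The sponsor's clinical team must reconcile the Section 6.2.2 text with the last row of Table 3. Either both should carry one recovery threshold, or the section should state which rule prevails and what the exception clause covers. The decision should be communicated to all sites. This review does not say which threshold is right.

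The cost is a wording change through the amendment procedure in Section 9.8 and a memo to sites. There is no statistical cost.
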